### 5.6 Monitoring for incident HCV infection

Participants who had a negative HCV RNA PCR at baseline (or whose HCV RNA PCR became negative without treatment), who subsequently have a positive HCV RNA PCR will be considered incident HCV infections, but not reinfections.

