#### 1.4.3 Usual Care Arm

During Part A: Participants randomized to the usual care arm will have a same-day lab draw for confirmatory HCV RNA testing. Those who test RNA positive will be referred to local clinic or community based HCV medical providers.

Participants will be contacted monthly via telephone for a short questionnaire. Scheduled study visits will occur at study weeks 12, 24, 36 and 48 for semi-structured interviews and HCV RNA testing.

During Part B: no participants will be assigned to the usual care arm

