## 5.5 Monitoring for reinfection

Participants in the intervention arm who receive treatment will have two post-treatment HCV RNA PCR tests, at 24 and 48 weeks, to monitor for re-infection after treatment completion. Participants who did

not receive treatment, either because of HCV-negative status or because of other reasons, will have HCV RNA PCR testing at 24 and 48 weeks. All participants in the control arm, regardless of HCV RNA status, will have HCV RNA PCR testing at 24 and 48 weeks, but it is expected that these may not be “post-treatment,” as we expect treatment initiation to be delayed for the control participants.

True reinfection will be defined as a positive HCV RNA PCR with a different HCV genotype, occurring anytime after a documented SVR 12 (negative HCV RNA PCR 12 weeks or more after treatment completion).

Participants who (1) did not have a documented SVR 12 but did have a documented end-of-treatment response or SVR 4, and subsequently have a positive HCV RNA PCR OR (2) have a positive HCV RNA PCR after documented SVR12 with the same genotype as the initial infection, will be classified as possible reinfections. These participants will then be reclassified as either true reinfections or relapses based on viral sequencing of their baseline HCV infection compared to subsequent positive HCV RNA PCRs.

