### 5.8 Storage of samples for future analyses

All participants in part A will have plasma samples and/or dried blood spots (in event phlebotomy unavailable or unsuccessful) stored at the Weill Cornell Clinical and Translational Science Center laboratory. Future analyses will include HCV genotyping in instances of reinfection or treatment failure, and phylogenetic analyses of HCV virus. Participants in Part B will have samples stored when feasible, which we expect to be uncommon as laboratory testing will largely occur at community sites.

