## 6.8 Incident hepatitis C infection

Participants with incident hepatitis C as defined in section 5.6 will be given options for treatment of their HCV. These may include enrollment in other studies (if eligible) or referral to an external provider for management of their HCV.

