## 8.3 Data Analysis

### 8.3.1 Analysis of clinical outcomes data

For the primary analysis, after the completion of part A, we will compare the proportion of patients who achieve SVR12 in each arm using Chi-square or Fishers’ exact testing, using an intention-to-treat approach in which participants are analyzed in the group to which they are randomized. Participants with negative confirmatory HCV RNA PCR tests on study entry will not be included in the analysis.

For secondary analyses, we will:

- Compare the proportion of patients who achieve end-of-treatment response using Chi-square or Fishers’ exact testing
- Compare the proportion of patients who complete treatment, using Chi-square or Fishers’ exact testing
- Compare the proportion of patients who have HCV reinfection, using Chi-square or Fishers’ exact testing
- Describe adherence for participants in the Intervention arm only
- Describe demographic, clinical and behavioral factors for participants who have HCV reinfection or incident HCV infection

We will also perform the same analyses using an “as-treated” approach, in which participants in the intervention arm will not be included if they failed to initiate HCV treatment, or discontinued treatment for reasons clearly unrelated to the treatment intervention (e.g. relocation, incarceration).

After the completion of part B, we will compare the proportion of patients who achieve SVR12 in each Part B telemedicine to (1)Part A intervention (2) Part A control, using Chi-square or Fishers’ exact testing, using an intention-to-treat approach in which participants are analyzed in the group to which they are randomized. Participants with negative confirmatory HCV RNA PCR tests on study entry will not be included in the analysis.

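### Section 5.6 counts an untreated positive–negative–positive RNA sequence as a new HCV infection without confirming clearance or comparing viruses; the effect is confined to a descriptive analysis and the Section 6.8 label

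*Combined protocol and SAP*

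**What the plan says.** Section 5.6 defines incident infection for two groups in one sentence. The first is people RNA negative at baseline who later turn positive. The second is people positive at baseline: "or whose HCV RNA PCR became negative without treatment), who subsequently have a positive HCV RNA PCR will be considered incident HCV infections". For the second group it sets no number or spacing of negative results and no comparison of the later virus with the baseline virus. It adds that these cases are not reinfections.

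Section 5.5 handles the parallel question for treated people. A positive result after SVR12 with a different genotype is a true reinfection. A same-genotype positive after SVR12, or a positive in someone who "did not have a documented SVR 12 but did have a documented end-of-treatment response or SVR 4", is only a possible reinfection, and such cases are "reclassified as either true reinfections or relapses based on viral sequencing of their baseline HCV infection compared to subsequent positive HCV RNA PCRs".

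The incident label is used in two places. Section 8.3.1 plans to "Describe demographic, clinical and behavioral factors for participants who have HCV reinfection or incident HCV infection", and Section 6.8 says that "Participants with incident hepatitis C as defined in section 5.6 will be given options for treatment of their HCV".

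Section 5.8 stores samples from all Part A participants and says "Future analyses will include HCV genotyping in instances of reinfection or treatment failure, and phylogenetic analyses of HCV virus". It does not link either analysis to the Section 5.6 label.

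**The concern.** A positive RNA result after a negative one can mean a new virus or the original one. Section 5.5 recognises this and resolves it. Its route requires a documented end-of-treatment response, SVR4 or SVR12, so an untreated person cannot enter it. Section 5.6 then decides the same ambiguity automatically in favour of a new infection.

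Two kinds of record would be misclassified:

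- An untreated person with the same virus throughout who has one undetectable result between positive ones.
- A control who was treated elsewhere, did not report it, and relapsed. Control treatment status is self-reported (monthly contacts in 1.4.3 and 2.2.3, interviews in 3.0), and records are requested only from those known to have started treatment.

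At stake is the description in 8.3.1 of who acquires HCV. With few events expected, one or two persistent infections could be a sizeable part of the group described, and the rule calls for no data from which a reader could notice.

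**Working it through.** **The plan's own figure.** The documents give no number for incident infection. The nearby SVR12 power statement (41% v 78%, 27 per arm, 80% power) reproduces at 80.9% with the usual two-sided 0.05 normal approximation, but it does not bear on this point.

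**Does another section repair the rule?** No. Section 5.5 is closed to untreated people. Section 5.8 names reinfection and treatment failure for genotyping, and phylogenetics only in general terms. The schedules in Section 5 have an additional-tests column for reinfection or relapse and none for incident infection. Section 2.2.3 permits extra testing after abnormal results but does not make the label depend on it.

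**Inputs for size**

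- Untreated controls, from 8.1: 12% uptake gives 27 × 0.88 = 23.8, about 24. A control SVR12 of 11/27 leaves at most 27 − 11 = 16.
- Untreated intervention participants, upper bounds from 8.1: 27 × 0.15 = 4.05 at 85% SVR12, or 27 − 21 = 6 at 78%.
- Control RNA draws after entry: the synopsis has four, "Scheduled study visits will occur at study weeks 12, 24, 36 and 48 for semi-structured interviews and HCV RNA testing", as does the Part A schedule (5.1). Section 3.0 has three (12, 24, 48) and Section 5.5 has two (24, 48).
- Intervention RNA draws: six in the Part A schedule (4, 12, 16, 24, 36, 48). Section 5.5 gives untreated intervention participants two (24, 48).
- q, the chance of an undetectable result per draw in a persistently infected person: **assumed**, 1% and 5%. Independence between draws and full attendance are also assumed.

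**Formula.** With n draws, a false event is avoided only if no undetectable draw is later followed by a detectable one, that is, if any undetectable draws all come last. So

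p = 1 − Σ(k=0..n) (1−q)^(n−k) q^k = 1 − [(1−q)^(n+1) − q^(n+1)] / (1−2q).

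For n = 4 and q = 0.01: 1 − 0.99^5/0.98 = 1 − 0.9704 = 0.0296.

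**Expected false events in usual care (p × number untreated)**

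| Control draws | p, q = 1% | 16 / 24 untreated | p, q = 5% | 16 / 24 untreated |
|---|---|---|---|---|
| 24, 48 (5.5) | 0.99% | 0.16 / 0.24 | 4.75% | 0.76 / 1.14 |
| 12, 24, 48 (3.0) | 1.98% | 0.32 / 0.48 | 9.50% | 1.52 / 2.28 |
| 12, 24, 36, 48 (1.4.3, 5.1) | 2.96% | 0.47 / 0.71 | 14.02% | 2.24 / 3.37 |

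For the intervention arm on six draws, p is 4.89% at q = 1% and 22.4% at q = 5%. With 4.05 to 6 untreated this gives at most 0.2–0.3 and 0.9–1.3 events.

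**Usual care's share.** For small q, false events are roughly proportional to untreated people × visits at which a negative can still be followed by a positive (n − 1).

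| At-risk visits, control : intervention | 23.8 v 4.05 untreated | 16 v 6 untreated |
|---|---|---|
| 1 : 1 (5.5 for both) | 85% | 73% |
| 3 : 5 (5.1 for both) | 78% | 62% |
| 2 : 5 (3.0 for control, 5.1 for intervention) | 70% | 52% |

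Example: 16×2 / (16×2 + 6×5) = 32/62 = 52%. Pairing the Section 5.5 weeks for controls with the 5.1 weeks for intervention (1 : 5) would give 54% or 35%, but Section 5.5 sets the same two weeks for untreated people in both arms.

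**The case against.** The strongest reply is that little depends on the label. In 8.3.1 incident infection appears only in a descriptive item, with no rate, estimate or test between arms. These cases are outside the tested reinfection comparison by definition, outside the denominator of secondary outcome 4 in Section 1.7 (SVR12 achieved or RNA negative at baseline), and irrelevant to SVR12. All of this stands.

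A reader might infer that the rule biases the trial against usual care by inflating its new infections. The documents do not support that: no arm comparison of incident infections is planned, untreated intervention participants fall under the same rule, and the Part A schedule tests that arm more often.

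A reader might also take the top of the table as the expected count. That needs the highest draw schedule, the lowest control uptake, full attendance, the full 27 per arm and a q for which the documents offer no support. Part A closed on enrolment to 1 March 2020, with power acknowledged to be reduced.

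Finally, becoming negative without treatment could be read as established spontaneous clearance, and Section 5.8 foresees phylogenetic work. Both would help if 5.6 said so. As written, one undetectable draw satisfies it, and no sequencing result can change the label.

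**Conclusion.** The point holds as a defect in a classification rule with limited reach. Followed literally, Section 5.6 can record a new infection when the virus is unchanged, although Section 5.5 already has the means to tell the two apart. The consequence is possible contamination of the 8.3.1 description and of the group to which Section 6.8 refers.

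Under the stated assumptions, usual care would contribute about 0.2 to 0.7 false events at q = 1% and 0.8 to 3.4 at q = 5% at the target size, and fewer at actual enrolment. Its share of false events is probably a majority, about 52% to 85% on the plan's uptake and SVR12 assumptions and its differing visit schedules. That share is an inference: the counts of untreated people are partly upper bounds, and the low end is barely over half. The true frequency of transient negatives is unknown from the documents.

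**What to change.** In Section 5.6, separate two groups:

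- **(a)** RNA negative at baseline, later positive: incident infection, as now.
- **(b)** RNA positive at baseline, negative without reported treatment, later positive: *possible new infection*. Compare the later positive sample with the stored baseline sample by the Section 5.5 sequencing step. Count a new infection only if the viruses differ; otherwise record persistent infection, or relapse if outside treatment comes to light.

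Where no pair of samples can be sequenced, report the event as unclassified. This will be common in Part B, where Section 5.8 expects stored samples to be uncommon. A rule of two consecutive negatives is not a dependable substitute: it cannot operate on the week 24 and 48 draws in Section 5.5, and on the Section 3.0 schedule only negatives at 12 and 24 followed by a positive at 48 would qualify.

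In 8.3.1, report (a), (b) and reinfections separately. Because Section 6.8 takes its population from 5.6, the two sections should be reconciled so that it is clear which group is meant. The control-arm RNA weeks in 1.4.3, 3.0, 5.1 and 5.5 should be reconciled too.

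The cost is a few sentences and the sequencing of a few stored Part A samples, with no change to visits or to the primary analysis. The downside is that some events, including some genuine new infections, will stay unclassified.

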### 5.7 Reinflection Prevention Counseling

All HCV RNA positive participants in the intervention arm will be scheduled for a harm reduction counseling session focusing specifically on HCV reinfection prevention. Participants will receive a condensed version of Staying Safe (Ssafe). Ssafe is an innovative, strengths-based, socio-behavioral HCV prevention intervention for young PWID. Ssafe addresses multi-level “upstream” determinants of risk that occur relatively early in the causal chain of risk, including eco-social conditions, social relations and risk situations, in addition to directly targeting risky injection practices. Ssafe trains and motivates PWID to better manage drug use to avoid situations and practices that promote risky injection (e.g., “binging” on drugs), and to implement health-protective behaviors (e.g., promoting risk-reduction norms in injection networks). Additionally, referral to existing LESHRC services will be encouraged including syringe exchange, overdose prevention, substance use treatment, and social services

### 5.8 Storage of samples for future analyses

All participants in part A will have plasma samples and/or dried blood spots (in event phlebotomy unavailable or unsuccessful) stored at the Weill Cornell Clinical and Translational Science Center laboratory. Future analyses will include HCV genotyping in instances of reinfection or treatment failure, and phylogenetic analyses of HCV virus. Participants in Part B will have samples stored when feasible, which we expect to be uncommon as laboratory testing will largely occur at community sites.

## 6. Clinical Management Issues

### 6.1 Chronic Kidney disease

Estimated GFR will be calculated based on the CKD-EPI formula based on baseline laboratory testing. Participants with chronic kidney disease stage 4 or 5, defined as estimated GFR < 30 mL/min, or those reporting hemodialysis will be discontinued from the study. Participants with any amount of chronic renal impairment will be counseled about the potential for a higher degree of side effects that may be observed in these groups, in accordance with national guidelines

## 6.2 Cirrhosis and severe liver disease

Participants will have laboratory assessment for cirrhosis via FIB-4 as described in section 5.2. Participants with decompensated cirrhosis by physical exam, as determined by the treating physician on the basis of variceal bleeding, ascites, hepatic encephalopathy, or jaundice, will be discontinued from the study and referred to a hepatology specialist for co-management of cirrhosis and HCV. Participants with compensated cirrhosis, after completion of HCV treatment, will be referred to primary care or hepatology for ongoing evaluation of cirrhosis including HCV screening.

## 6.3 Incident HIV infection

Participants who are initially HIV negative but seroconvert to HIV during the study will remain included in the study. They will be analyzed with the arm in which they were randomized. They will be offered to linkage to HIV primary care at an HIV provider local to them.

## 6.4 Pregnancy

Participants who initially have a negative pregnancy test but become pregnant during the study and are already on HCV treatment will be told the potential risks and benefits regarding continuation, and a joint decision between participant and provider will be made regarding continuation of therapy. Participants who are found to be pregnant before initiating therapy will not be started on treatment but remain in the study. Participants who become pregnant after treatment completion will remain in the study.

## 6.5 Hepatitis B Reactivation

Participants who have evidence of chronic HBV infection (positive HBV surface antigen) will be monitored for signs of reactivation including elevation of liver enzymes or clinical symptoms such as jaundice. Those who do have signs of reinfection will be provided with facilitated referral to an HBV treatment provider for treatment. Those who do not have evidence of HBV immunity (negative HBV surface antibody and negative HBV surface antigen) will be referred for HBV vaccination.

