#### 2. Section 1.4: Intervention Arm

**Change:** For participants entering in Part B, the co-located rapid start intervention will be converted to telemedicine rapid-start intervention. Consented participants will have same-day or next-day telemedicine visits with a hepatitis C provider and baseline blood testing will be arranged on a personalized basis utilizing convenient community-based laboratory facilities (including current co-located SSP and commercial laboratories). For participants found to be HCV PCR positive, personal delivery or pick-up of a 28-day supply of sofosbuvir/velpatasvir (Epclusa®) will be

arranged. Telemedicine visits will be arranged two weeks after treatment delivery. For participants who confirm treatment initiation, side effects will be assessed, delivery/pick-up of the final 56-day of medication will be arranged, and week 4 monitoring labs will be offered (no longer required) and arranged.

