### 6. **Section 5.1 :** Schedule of Study Events

**Change:** Week 4 and Week 8 laboratory draws are now changed to optional, to minimize travel and physical contact. Monitoring labs for re-infection have been eliminated, and re-infection will not be analyzed for the telemedicine cohort. Instead, individuals will reach the study endpoint at either SVR 12 or at week 48, whichever comes first. The frequency of medical visits will be unchanged but physical exams will no longer be performed except as possible through telemedicine. Weekly telephone or video check-ins will also continue.

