#### 1.4.2 Intervention Arm

In Part A: Participants randomized to the intervention arm will have a same-day visit with a study physician. Those who are interested in being treated for their HCV, and have no contraindication, will (a) have standard of care baseline laboratory testing drawn and be given a one-week ‘Starter-Pack’ (7 day supply) of sofosbuvir 400mg/velpatasvir 100mg. Subsequent supplies of DAA therapy will be distributed to HCV RNA test positive participants as one 21-day and one 56 day supply to complete a 12-week treatment course. Those participants with negative confirmatory HCV RNA testing will be contacted via telephone and instructed not to begin the medication, and will not be given additional medication supplies.

Participants will be contacted weekly while receiving sofosbuvir/velpatasvir by text message to assess adherence, potential adverse effects, and offered other tele-support as needed. Scheduled study visits will occur at 4 weeks, upon treatment completion or discontinuation (study week 12), study week 16 (corresponding to SVR4), study week 24 (corresponding to SVR12), study week 36, and study week 48. Each study visit will consist of laboratory testing, semi-structured interview, and physician visit. Additional medical visits may be scheduled at the participants’ request. Additionally, each participant will be scheduled for a one-time counseling session for prevention of reinfection during their course of treatment. Referral to harm reduction and/or opioid substitution treatment programs will be provided for interested participants, but utilization of these services is not a condition of enrollment in the study or of HCV treatment provision.

In Part B: Participants will be enrolled in the telemedicine arm, and will have a same-day or next-day telemedicine visit with the hepatitis C provider. Initial evaluation will be either via telephone, video, or in-person at the syringe service program depending on patient preference. Blood testing will be arranged at local community laboratory facilities. Participants with positive HCV RNA will have delivery of a 28 day supply of sofosbuvir/velpatasvir, and a 56 day supply after completion. Weekly check-ins will occur by phone, and participants will have clinical laboratory monitoring at week 4 (optional), week 12, every 12 weeks thereafter until completion of follow up. Participants will complete a short structured survey at weeks 0, 12, 24, 36, and 48, also over video or telephone.

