### 2.2.3 Schedule of follow up and monitoring

In keeping with the overall purpose of the intervention, medical visits will be limited to only those that are necessary for successful treatment. Current 12-week regimens are well-tolerated with minimal toxicity in most patients. At enrollment, HCV RNA PCR, chemistry, liver enzymes, blood count, HIV status, HBV status, and a test for liver fibrosis (imaging or laboratory), and a pregnancy test (for female patients) will be ordered. HCV RNA positive patients in the intervention arm will be asked to start medications after results of laboratory testing are reviewed. After medication start, one laboratory visit will be scheduled at 4 weeks to monitor liver enzymes and assess for on-treatment response via HCV PCR. Subsequently, liver enzymes and HCV PCR will be drawn at the end of treatment and 12 weeks of follow up to confirm response and cure. The purpose of the final monitoring visit will be to assess for HCV reinfection. Additional testing may be done if deemed necessary by clinical staff or to follow-up on abnormal results. Apart from the 4 study visits, the participants will each be contacted at least monthly by secure text message or phone call, and additional visits scheduled only if requested by the participant or deemed necessary by clinical staff. Participants randomized to the control arm, and HCV-negative participants in the intervention arm, will have text message or phone check in every month to determine their HCV treatment status., and study visits every 12 weeks for questionnaire, interview, and HCV RNA testing.

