### 5.2.4 Hepatitis B Panel

HBV testing will consist of HBV surface antigen, HBV surface antibody, HBV core antibody, HBV envelope antibody. HBV testing will be performed on all intervention participants at study entry.

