#### 7.2 Study withdrawal and discontinuation

Participants may be withdrawn from the study at any time at their own request. They may also be discontinued from the study if, at any time, they are considered by study investigators to be unlikely to be able to participate in necessary follow up (e.g. due to severe illness, incarceration, change of residence). However, in keeping with the overall goal of the intervention, participants who are unwilling to partake in interviews or questionnaires, or undergo blood tests, will still remain in the study.

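### Part B requires no liver enzyme test between entry and week 12, even for participants with hepatitis B, whereas Part A requires one at week 4

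*Combined protocol and SAP*

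**What the plan says.** Section 5.2.4 establishes hepatitis B status at the start: "HBV testing will be performed on all intervention participants at study entry". Hepatitis B infection is not an exclusion criterion (1.3.2), so HBsAg-positive participants can be treated. Under 6.5 they "will be monitored for signs of reactivation including elevation of liver enzymes" or by symptoms such as jaundice, and those with signs are referred to a hepatitis B provider. The section gives no dates and no separate rule for Part B.

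The enzyme schedule differs between the parts:

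- **Part A.** Section 2.2.3 says that "one laboratory visit will be scheduled at 4 weeks to monitor liver enzymes and assess for on-treatment response via HCV PCR". The Part A schedule (5.1) lists this hepatic panel for RNA-positive intervention participants without an optional mark.
- **Part B.** Section 1.4.2 gives "clinical laboratory monitoring at week 4 (optional), week 12, every 12 weeks thereafter until completion of follow up". Section 3.0 also makes the week 4 tests optional. In the Part B schedule (5.2), the week 4 hepatic panel carries the optional-draw mark and the week 12 panel does not. The amendment summary agrees: in item 2, "week 4 monitoring labs will be offered (no longer required) and arranged"; in item 6, the early "laboratory draws are now changed to optional, to minimize travel and physical contact".

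None of these places makes an exception for HBsAg-positive participants. Two general provisions also bear on the point. Section 2.2.3 says that "Additional testing may be done if deemed necessary by clinical staff", and 7.2 says that "participants who are unwilling to partake in interviews or questionnaires, or undergo blood tests, will still remain in the study".

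**The concern.** HBsAg-positive participants are the one subgroup to whom the protocol promises monitoring for reactivation, and referral under 6.5 depends on signs being found. In Part B, the only scheduled enzyme test between entry and week 12 was made optional for everyone, and 6.5 was not adapted.

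Check-ins by telephone or video can pick up symptoms. They cannot detect an enzyme rise without symptoms, and under the amendment physical examination happens only as far as telemedicine allows. An enzyme result before week 12 therefore depends on the participant accepting an optional draw or on a clinician choosing to order one.

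Drug supply no longer prompts a laboratory check either. In Part A the remaining medication was handed out at the week 4 visit with its laboratory evaluation (3.0). In Part B the final 56 days of drug are arranged at a telemedicine visit two weeks after the first delivery (0.2, item 2). A participant can thus take most or all of the course with no required enzyme test.

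**Working it through.** The check is calendar arithmetic on the visit windows, with week 0 as day 0. The documents give windows rather than day ranges.

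**Inputs**
- Week 4 window: −7 to +14 days (5.1 and the Part B schedule in 5.2).
- Week 12 window: +7 days (same places).
- Part B drug supply: 28 days, then 56 days (1.4.2).

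**First required hepatic panel after entry**

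| | Nominal day | Earliest | Latest |
|---|---|---|---|
| Part A, week 4 | 28 | 28 − 7 = 21 | 28 + 14 = 42 |
| Part B, week 12 | 84 | 84 | 84 + 7 = 91 |
| Shift (days) | 56 | 63 | 49 |

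Across the windows the shift runs from 84 − 42 = 42 days to 91 − 21 = 70 days.

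**Position relative to treatment.** The supply lasts 28 + 56 = 84 days. If study weeks count from the first dose, the first required panel falls on treatment day 84–91. If they count from entry and drug arrives *d* days later, it falls on day 84 − *d* to 91 − *d*. The documents do not give *d*. Assuming 7 to 14 days:
- *d* = 7: treatment day 77–84
- *d* = 14: treatment day 70–77

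**Longest interval without a required panel, up to week 12**
- Part B now: 91 days (entry to the latest week 12 date).
- With week 4 required: the larger of 42 (entry to the latest week 4 date) and 91 − 21 = 70 (earliest week 4 to latest week 12), so 70 days, as in Part A.

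Requiring week 4 brings the latest permitted first test forward by 91 − 42 = 49 days and shortens the longest interval by 91 − 70 = 21 days.

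**Sensitivity to reading.** If the week 12 window was meant as plus or minus 7 days, the Part B range becomes day 77–91; the nominal shift stays at 56 days. The column headings of the Part B table are displaced in the extracted text, but the row pattern matches Part A, and 1.4.2 and 3.0 confirm that week 4 is optional.

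**The case against.** The strongest reply is that 6.5 is already the specific rule for HBsAg-positive participants and was not relaxed for Part B. If it obliges staff to check enzymes, a general optional mark does not cancel that duty, and 2.2.3 gives the means to fulfil it. If symptoms alone suffice, the weekly check-ins meet it. Either way there is no outright contradiction, and 6.5 lacks dates in Part A too. This is fair as far as it goes. But in Part A the general schedule supplies a required early test and in Part B it does not, while the extra testing in 2.2.3 is discretionary.

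Other points on that side:

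- **Week 4 tests are still offered and arranged, and blood tests may be declined in both parts.** This stands. The contrast is between a default draw and an offered one, not between a certain test and none.
- **The 42 to 70 day range pairs opposite ends of the windows.** Also fair: matching ends gives 49 to 63 days, 56 at nominal dates.
- **No harm is shown.** The documents do not say when reactivation occurs, so it cannot be claimed that a week 4 panel would catch it.
- **The group may be empty.** Section 3.0 gives 72 antibody-positive participants over both parts; at the 75% viraemia in 8.1, that is 72 × 0.75 = 54. If 1% to 5% were HBsAg-positive (an assumption), 54 × 0.01 to 54 × 0.05 gives about 0.5 to 2.7 people in the whole study, and fewer in Part B. This limits the importance of the point but does not remove the gap.
- **The change was a deliberate pandemic trade-off.** The stated aim was less travel and contact. Nothing in the documents weighs that aim against 6.5, and a narrow exception preserves it for everyone else.

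**Conclusion.** The concern holds, as a minor point with a cheap safety improvement. For HBsAg-positive participants in Part B, the protocol requires no enzyme test after entry until day 84–91, against day 21–42 in Part A: 56 days later at nominal dates, and close to or past the end of the 84-day supply. This rests on the windows as printed and on week 0 being day 0. The treatment-day range of 70–84 also assumes a delivery delay of 7 to 14 days. The conclusion is about what the protocol requires. It does not say that no earlier test will happen, how many people are affected, or that one panel would detect reactivation.

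**What to change.** Require the already scheduled week 4 hepatic function panel for HBsAg-positive Part B participants on treatment:

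1. **Part B schedule (5.2), hepatic function panel row, week 4.** Add a footnote: *Required, not optional, for HBV surface antigen-positive participants who have started SOF/VEL (window −7/+14 days).*
2. **Section 1.4.2, Part B.** Qualify the optional week 4 entry: *optional, except that the hepatic function panel is required for HBV surface antigen-positive participants who have started SOF/VEL.*
3. **Section 3.0.** Add the same exception where week 4 testing is made optional.
4. **Section 6.5.** Add: *In Part B this monitoring includes the week 4 hepatic function panel.*

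The drug supply rule, and the optional status for all other participants, stay as they are.

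The cost is one footnote, three short insertions and one community laboratory trip for each affected participant, which runs slightly against the amendment's aim of reducing travel and contact. Because 7.2 keeps people who decline blood tests in the study, the rule excludes no one. For the same reason it changes the default from offered to required and cannot guarantee the test.
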